
Schedule of Visits and Assessments: Months 3, 6, 9 and 12
	
At Months 3, 6, 9 and 12 the following assessments will be performed before treatment administration (unless specified otherwise):
 
 • Informed consent/assent at Month 6 for patients continuing treatment • Physical examination • Vital signs • Neurological examinations • ICARS (video recording required) • CGI-S • CGI-C • VABS • EQ-5D-5L • C-SSRS • ECG • Routine laboratory tests on the diverted blood sample

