- Patients originally randomized to the Placebo group (Group 3) will be re-randomized (randomization to be done at baseline) in equal proportions (1:1) to receive either the EDS-EP ~5-10 mg DSP/ infusion or ~14-22 mg DSP/infusion (or the remaining dose of EDS-EP, if one of the doses has been eliminated following the Interim Analysis), as follows:
 - Following 6 months of treatment, one third of the placebo patients will be switched to treatment with EDS-EP, as described above;
 - After 9 months of treatment, one third of the placebo patients will be switched to treatment with EDS-EP, as described above;
- At 12 months, all remaining placebo patients who continue in the open-label phase will receive treatment with EDS-EP, as described above.

Visit 9 (Month 6) evaluations from the Initial Treatment Period will serve as the Baseline assessments for the Extension Treatment Period. Once these are completed, patients will have blood drawn for the EDS encapsulation procedure and will receive the infusion as before. Vital signs and a physical examination will be performed after dosing.

Subsequently in the Extension Treatment Period, EDS-EP infusions will be performed at Months 7, 8, 9, 10 and 11 (Visits 10 – 14), after which vital signs (including body weight and height in triplicate) and a physical examination will be performed. The C-SSRS assessment will also be performed at each of these visits. A blood sample will be collected for measurement of serum creatinine at Months 7, 8, 10 and 11, whereas creatinine will be part of the routine laboratory tests at Months 9 and 12. In addition, on Month 9 (Visit 12), all efficacy assessments (ICARS, CGI-C, CGI-S, VABS, and QoL) will be done prior to the infusion, and the neurological examination, routine laboratory tests and the ECG will be repeated. Upon completion of the EDS process 2.5 mL of the processed blood will be collected for measurement of DSP concentration and a CBC.

At Months 6 and 9, in selected centers, a 5-mL sample will be taken from the EryKit_01 bowl at the end of the process to assess RBC osmotic resistance. At Months 6 and 9, a hemolysis panel will be done pre- and post-infusion.

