Change from baseline will be calculated by using the following formula =

(mICARS Score at Visit 6 ("Month 3") - Baseline mICARS Score)

(mICARS Score at Visit 9 ("Month 6") - Baseline mICARS Score)

Extension Treatment Period

For subjects randomized to EDS-EP and placebo subjects who are not switched to EDS-EP (original treatment assignment), the change from baseline will be calculated by using the the last assessment prior to first dose as baseline. For the placebo subjects who are switched to EDS-EP at either Visit 9 ("Month 6") or Visit 12 ("Month 9"), the last mICARS Score prior to the switch will be used as baseline. Change will be calculated as follows:

(mICARS Score at Visit 12 ("Month 9") - Baseline mICARS Score)

(mICARS Score at Visit 15 ("Month 12") - Baseline mICARS Score)

The Clinical Global Impression (CGI-C and CGI-S [structured])

The Clinical Global Impression (CGI) consists of two 7-point, clinician-rated, Likert-type scales assessing change from baseline (CGI-C) and severity of neurological symptoms (CGI-S [structured]) (Guy, 1976).

In the current study, an overall assessment of the change in the subject's neurological symptoms of AT, compared to the status at baseline, will be made using the CGI-C. CGI-C scores range from 1 (very much improved) through 7 (very much worse). CGI-C is assessed at Visit 6 ("Month 3") and Visit 9 ("Month 6") during the initial treatment period, and at Visit 12 ("Month 9") and Visit 15 ("Month 12") of the extension treatment period.

In addition, the severity of neurological symptoms at baseline and at each subsequent time point will be assessed using the CGI-S (structured). No version of the CGI-S exists which has been specifically adapted for use in AT patients; therefore, a structured 5-point version was developed which takes into account the severity of the following symptoms of AT: ataxia (walking), dysarthria, dysmetria, extrapyramidal symptoms (chorea, myoclonus, dystonia, and tremor), and eye movements (Nissenkorn, 2015). Ratings of none, mild, moderate, severe, and very severe are selected based on the level of symptomatology. CGI-S (structured) is assessed at Visit 6 ("Month 3") and Visit 9 ("Month 6") during the initial treatment period, and at Visit 12 ("Month 9") and Visit 15 ("Month 12") of the extension treatment period.

Vineland Adaptive Behaviors Scale (VABS)

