Functional intelligence generally is defined as one's ability to behave adaptively in daily life. Specifically, it includes the person's ability to express and comprehend language, behave appropriately in interpersonal situations, understand and use social behaviors, protect himself/herself, and care for himself/herself, in terms of personal hygiene and domestic independence. Although several scales and observation systems for measuring adaptive behavior have been developed since the 1940s when the construct of adaptive behavior was formally introduced, one of the most widely accepted scales is the Vineland Adaptive Behavior Rating Scales (VABS) (Sparrow, 2005).

The VABS is used primarily with children and adolescents from birth to age 18 years but may be used for adults suspected of having a mental handicap based on obtained IQ. The scale measures adaptive behavior in four major domains, Communication, Daily Living Skills, Socialization, and Motor Skills. These domains include several subdomains, as follows:

- **Communication:** Receptive, Expressive, Written
- **Daily Living Skills:** Domestic, Personal, Community
- **Socialization:** Interpersonal Relationships, Play & Leisure, Coping Skills
- **Motor Skills:** Gross, Fine.

VABS is assessed at Visit 1 (Day 0), Visit 6 ("Month 3"), and Visit 9 ("Month 6") during the initial treatment period, and at Visit 12 ("Month 9") and Visit 15 ("Month 12") of the extension treatment period. The Visit 1 result will be used as the baseline score. For the placebo subjects that switched to EDS-EP at or after Visit 9 ("Month 6"), the last assessment prior to treatment with EDS-EP will be used as baseline for the comparisons to Visit 12 ("Month 9") and Visit 15 ("Month 12").

EQ-5D-5L Quality of Life (QOL) scale

The EQ-5D-5L is assessed at Screening, Visit 1 (Day 0), Visit 6 (“Month 3”), and Visit 9 (“Month 6”) during the initial treatment period, and at Visit 12 (“Month 9”) and Visit 15 (“Month 12”) of the extension treatment period. The Visit 1 result will be considered the baseline score. For the placebo subjects that switched to EDS-EP at or after Visit 9 (“Month 6”), the last assessment prior to treatment with EDS-EP will be used as baseline for the comparisons to Visit 12 (“Month 9”) and Visit 15 (“Month 12”).

C-SSRS

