For the extension treatment period, the change from baseline will be the change from the last assessment prior to first infusion in the study except for the placebo subjects who switch to EDS-EP at Visits 9 and 12 (‘‘Month 6’’ and ‘‘Month 9’’, respectively). For these subjects who are switched, the baseline will be the assessment just prior to the switch. The change will be summarized for Visit 12 (‘‘Month 9’’) and Visit 15 (‘‘Month 12’’), using LOCF and OC. Because

of the small sample size and the switch from placebo to EDS-EP, no formal statistical comparisons of treatment groups will be made.

For the FAS only, the mean mICARS score will be plotted over time during the initial treatment period with separate trend lines for each of the three treatment groups. This type of plot will be repeated for mean mICARS score and mean change from baseline in mICARS score over the entire study, with separate trend lines for the seven possible dosing schemes.

For the placebo subjects who switched to EDS-EP at Visit 9 (“Month 6”), the change seen during the initial treatment period, and the change between Visit 9 (“Month 6”) and Visit 15 (“Month 12”) will be compared with a paired t-test or a non-parametric equivalent. A comparison of the change over 3 months of placebo against 3 months of treatment will also be done using the first 3 months for the subjects who switch at Visit 9 (“Month 6”) and those who switched at Visit 12 (“Month 9”).

Sensitivity Analyses

The full ICARS will be analyzed using the same methods as for the primary analysis of mICARS. The nominal p-value will be presented, and no adjustments for multiplicity will be made.

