The VABS score at baseline and all visits during the initial treatment period and extension treatment period (Visit 6, Visit 9, Visit 12, and Visit 15) will be summarized using summary statistics

appropriate for continuous data by treatment group. The change from baseline to all visits will also be summarized and compared between treatment groups.

For the FAS only, the mean VABS score will be plotted over time during the initial treatment period with separate trend lines for each of the three treatment groups. This type of plot will be repeated for mean VABS score and mean change from baseline in VABS score over the entire study, with separate trend lines for the seven possible dosing schemes.

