5.4.2 Physical and Neurological Examination

Physical and neurological examinations will be performed at Screening, at Baseline (pre and post infusion) and prior to dosing at each of the monthly infusions (Visit 4 [“Month 1”], Visit 5 [“Month 2”], Visit 6 [“Month 3”] [also post infusion], Visit 7 [“Month 4”], and Visit 8 [“Month 5”]) and at the final visit (Visit 9 [“Month 6”] or at early discontinuation) during the initial treatment period. For subjects continuing in the extension treatment period, physical and neurological examinations will be performed pre- and post-infusion at Visit 9 (“Month 6”) and Visit 12 (“Month 9”), prior to dosing at each of the other monthly infusions (Visit 10 [“Month 7”], Visit 11 [“Month 8”], Visit 13 [“Month 10”], and Visit 14 [“Month 11”]) and at the final visit (Visit 15 [“Month 12”] or at early discontinuation).

If clinically significant abnormal findings are noted at Screening, the examination was to be repeated prior to Baseline. The physical examination will include an examination of general appearance, skin, neck (including thyroid), eyes and ears, nose, mouth, throat, lungs, heart, abdomen, back, lymph nodes, extremities and nervous system. Genital, urinary tract and rectal examinations are not required. The findings will be entered on the Physical Examination section of the CRF.

Physical and neurological examination data will be summarized by treatment period and visit according to the treatment received during the period. Shift tables will be provided for all values and separately for abnormal values (both clinically significant abnormalities and not). Baseline will be defined two ways, as the last assessment prior to the first infusion in the study (Baseline 1), and also as Baseline 1 for non-switch groups and as the last assessment prior to switch for placebo switchers (Baseline 2), and thus summaries will be repeated to reflect the use of each baseline definition.

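### Placebo patients switched at Month 9 get a Month 9 change of zero by construction, because the SAP makes their Visit 12 score its own baseline

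*SAP*

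**What the plan says.** **Baseline rule.** SAP Section 4 (ICARS, Extension Treatment Period) covers patients switched at Visit 9 and at Visit 12 with one rule: "the last mICARS Score prior to the switch will be used as baseline". It then defines change as Visit 12 minus baseline and Visit 15 minus baseline. Original EDS-EP patients and placebo patients who do not switch keep the assessment before the first dose.

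**Where it recurs.** SAP 5.3.1 states for mICARS: "For these subjects who are switched, the baseline will be the assessment just prior to the switch. The change will be summarized for Visit 12". SAP 5.3.3 (CGI-S and VABS) and 5.3.4 (EQ-5D-5L) repeat the rule. For VABS and EQ-5D-5L, Section 4 ties it expressly to that visit: "the last assessment prior to treatment with EDS-EP will be used as baseline for the comparisons to Visit 12". SAP 3.1 carries the mICARS methods over to the full ICARS and both rescored versions. None of these sections makes an exception for the visit at which the switch happens.

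**Timing.** The protocol synopsis says: "At Months 3, 6, 9 and 12 the following assessments will be performed before treatment administration". Protocol 11.2 says of Month 9 that "all efficacy assessments (ICARS, CGI-C, CGI-S, VABS, and QoL) will be done prior to the infusion", and Protocol 11.5.3 lists the scales under the pre-infusion procedures.

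**Use of the result.** For VABS, SAP 5.3.3 says: "The change from baseline to all visits will also be summarized and compared between treatment groups". CGI-S and EQ-5D-5L have the same sentence. SAP 5.1.10 makes the Month 9 and Month 12 comparisons descriptive, with p-values shown but not used for inference.

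**Safety.** SAP 5.4.2 defines two baselines, the original (Baseline 1) and the pre-switch one (Baseline 2), and runs the summaries with each. The extension efficacy sections have no such duplicate.

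**The concern.** A patient assigned to switch at Month 9 receives the first active infusion at Visit 12, after the Visit 12 scales. The last score before the switch is then the Visit 12 score. Subtracting it from itself gives zero whatever happened over nine months of placebo.

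The extension's primary objective is long-term EDS-EP versus placebo on mICARS, and Month 9 is the last visit at which two thirds of the placebo arm is still on placebo. Under the rule, half of those patients carry no information in the change variable and may carry false information. The same zeros enter the CGI-S, VABS and EQ-5D-5L between-group comparisons at Month 9 and the planned plots of mean change by dosing scheme.

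**Working it through.** **1. Reproduce SAP Table 5 (SAP 5.2.4; planned, no dropout).** Placebo starts with 60.
- Visit 9 to Visit 12: 60 − 60/3 = 40 on placebo, with 20 switched at Month 6 (10 + 10).
- Visit 12 to Visit 15: 40 − 40/2 = 20 on placebo, with 20 more switched at Month 9 (10 + 10).

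Both totals match the table. Month 9 switchers are 20 of the 40 patients on placebo up to Visit 12. The share stays one half if the numbers are scaled to the 175 enrolled.

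**2. Apply the rule to a Month 9 switcher.** Baseline = Visit 12 score, so change at Visit 12 = Visit 12 − Visit 12 = 0. If the Visit 12 score is missing but Visit 9 was observed, LOCF gives Visit 9 − Visit 9 = 0 as well.

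**3. If they are pooled with placebo.** Let the true nine-month placebo change be d, with SD s.
- Reported mean = (20 × d + 20 × 0)/40 = d/2.
- Reported variance = s²/2 + d²/4.

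The documents give no d, so 1 to 3 points is assumed. For s, 7 is taken from the SAP's planning range of 5.0 to 8.0.

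| d | Reported mean | Reported SD | Reported SE (n = 40) |
|---|---|---|---|
| 1 | 0.5 | 4.97 | 0.79 |
| 2 | 1.0 | 5.05 | 0.80 |
| 3 | 1.5 | 5.17 | 0.82 |

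With the study baseline the SE would be 7/√40 = 1.11. Using only the 20 informative patients it would be 7/√20 = 1.57. At d = 2, the reported SE is 0.58 for s = 5 (correct 0.79) and 0.91 for s = 8 (correct 1.26).

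**4. Effect on an active-minus-placebo difference.** Take a true difference of −3.0, the lower end of the SAP's planning range. The reported difference is (d − 3) − d/2 = d/2 − 3:
- placebo worsens by 2: −2.0
- placebo worsens by 3: −1.5
- placebo unchanged: −3.0
- placebo improves by 3: −4.5

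The direction of the bias depends on which way placebo moves.

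**5. Nominal p-values under pooling.** A simulation (20,000 runs, 60 active versus 40 placebo, unadjusted t-test, s = 7, no true effect) rejects at 0.05 in about 10% of runs when placebo changes by 2 points either way and about 20% when it changes by 3. With the study baseline it stays near 5%. This is a simple stand-in for the SAP's adjusted model.

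**6. If they are shown separately.** No dilution occurs. The two Month 9 switch groups have a Month 9 change of zero with no spread, their points on the change-from-baseline plots sit at zero, and the placebo column falls from 40 patients to 20.

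**The case against.** **The trial is decided elsewhere.** The Month 6 analysis and its error-controlled sequence do not use this rule, and SAP 5.1.10 and 5.3.6 make extension efficacy descriptive and exploratory. This stands, and it keeps the point from being a must-fix. A reader might infer that the trial's conclusion is at risk; the documents do not support that.

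**There may be no formal mICARS test to distort.** SAP 5.3.1 rules out formal group comparisons of mICARS in the extension, whereas SAP 3.1 and 5.1.10 plan comparisons. It would go too far to say that a planned mICARS test is corrupted. What can be said is that these sections conflict and that the descriptive summary is wrong either way.

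**Halving is not certain.** Table 5 describes exposure. The efficacy tables do not state their columns, and the shells are in a separate document. SAP 5.1.9 speaks of placebo numbers falling over the study, which fits pooling but does not settle it. The d/2 figure is therefore conditional.

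**A baseline visit is not normally a post-baseline visit.** One could read the rule as giving Month 9 switchers a change at Visit 15 only. The SAP does not say so, and Section 4 lists the Visit 12 comparison without distinction. On that reading they would still drop out of the Month 9 placebo change.

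**The raw data survive.** Observed scores by visit, score plots by scheme and the ICARS listing remain. This stands: the derived change is lost, not the observations.

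**Correlation tables.** A reader might infer that the Month 9 and Month 12 tables would pair a short mICARS change with a CGI-C rated against study entry. Only the table titles are given. They do not name CGI-C or the baseline, so this is a possibility only.

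**Conclusion.** The concern holds, at should-fix level. As written, and provided the Visit 12 scales are done before the infusion as scheduled, every Month 9 switcher has a Visit 12 change of zero on mICARS, full and rescored ICARS, CGI-S, VABS and EQ-5D-5L. Under planned numbers without dropout that is 20 of 40 placebo patients.

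The consequence depends on table layout: a halved placebo mean with understated spread if pooled, or empty information and a halved placebo column if separate. What suffers is the exploratory Month 9 summaries and change plots, and the descriptive between-group comparisons of CGI-S, VABS and EQ-5D-5L.

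The zero does not apply to all switchers. Month 6 switchers get a genuine three-month change at Visit 12, though it may stand beside nine-month changes. Patients switching in the open-label study are outside the rule. CGI-C has no subtracted baseline and is unaffected. For visits after the first active infusion the pre-switch baseline is reasonable.

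**What to change.** In SAP 4, 5.3.1, 5.3.3 and 5.3.4:
- Use the study baseline (Baseline 1) for every visit up to and including the switch visit. Month 9 switchers then count as placebo at Visit 12 with a true nine-month change.
- Use the pre-switch baseline only for visits after the first active infusion, and label those changes with time on active treatment (3 or 6 months).
- Alternatively, report extension efficacy with both Baseline 1 and Baseline 2, following SAP 5.4.2.
- State the column in which Month 9 switchers appear at Visit 12.

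Three points need reconciling at the same time. Protocol 11.2, 11.5.1 and note b to the schedule make Visit 9 the extension baseline, which differs from the SAP. SAP 5.3.1 must be squared with 3.1 and 5.1.10 on whether mICARS is compared between groups in the extension. If the Month 9 and Month 12 correlation tables include CGI-C, they should use the Baseline 1 mICARS change.

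The cost is SAP wording and some extra table programming. No new data are needed.

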5. STATISTICAL METHODOLOGY

5.1 Statistical and Analytical Issues

5.1.1 Statistical Methods

All eCRF data collected will be presented within data listings. The data listings will be sorted by treatment group, subject screening number, and visit. Any data collected on subjects that were screened but subsequently not randomized, will be presented within a non-randomized group.

The date format for all presentations will be 'ddmmyyyy'.

The treatment labels for all tables, figures, and listings will be:

- **Group 1, Low Dose:** EDS-EP ~5-10 mg
- **Group 2, High Dose:** EDS-EP ~14-22 mg

- **Group 3:** Placebo

All statistical methods will be based on the International Conference on Harmonization (ICH)-E9 Guidance for Industry "Statistical Principles for Clinical Trials".

Any changes concerning the statistical analysis will be documented in an amendment to the statistical analysis plan, and/or will be described in the CSR.

If any of the assumptions underlying the formal statistical methods proposed are violated during the analysis on the final data, an alternative, more appropriate, statistical method will be used and any changes will be documented in the statistical methods section of the clinical study report (CSR), including the rationale for use.

All data will be summarized by treatment group. In addition, where appropriate, a total column will be included to summarize all subjects. Where appropriate, data will be summarized by visit in addition to treatment group.

The three treatment groups will be compared for baseline/screening demographic data (i.e., age, gender, ethnicity, and race), region, and medical history data. Demographic and historical data will be assessed for potential differences between treatment groups by means of descriptive statistics. Demographic and baseline data will be presented using the FAS and Safety Population.

P-values will be rounded to four decimal places. P-values less than 0.0001 will be reported as "<0.0001" in tables. All statistical analyses will be performed using SAS® software version 9.4 or higher (Copyright, SAS Institute Inc. SAS and all other SAS Institute Inc. product or service names are registered trademarks or trademarks of SAS Institute, Inc., Cary, North Carolina, USA).

Categorical variables will be summarized using frequencies and percentages. Percentages will be presented to 1 decimal place. In cases where the percentage calculated is > 0% and < 0.1%, "<0.1%" will be presented against the count. In cases where the percentage calculated is 100.0%, "100%" will be presented without the decimal.

Continuous variables will be summarized using descriptive statistics (number of subjects with an observation [n], mean, standard deviation [SD], median, minimum [min], and maximum [max]) where $n \geq 2$. Unless otherwise specified, the mean and median for a continuous variable will be presented to 1 more decimal place than the original (raw) values and the SD will be presented to 2 more decimal places than the original values. The min and max will be presented to the same number of decimal places as the original values.

5.1.2 Handling of Dropouts

Subjects who discontinue treatment prematurely will be defined as dropouts. Those subjects who discontinue treatment prematurely but return for scheduled efficacy assessments at Visit 6 (“Month 3”), Visit 9 (“Month 6”), Visit 12 (“Month 9”), and Visit 15 (“Month 12”) will comprise the retrieved dropouts (RDO). Missing data will be handled as described below.

